Clinical Trial Protocol

Title of study: Skin Tag Removal Device; A Clinical Study to Determine Outcomes of Treating Adults with Acrochordons (Skin Tags)

NCT06463613

Date: 06/05/2025

Clinical Investigation Protocol

Title: Skin Tag Removal Device; A Clinical Study to Determine

Outcomes of Treating Adults with Acrochordons (Skin Tags)

Protocol: UKI-001

Sponsor: UK Innovations GP LTD

Version: 2

Date: TBD

Confidentiality Statement

This document contains confidential information that must not be disclosed to anyone other than the Sponsor, the Investigator Team, HRA, host organization, and members of the Research Ethics Committee and Regulatory Authorities unless authorized to do so.

Trial Title:	Skin Tag Removal Device; A Clinical Study to Determine Outcomes of Treating

Adults with Acrochordons (Skin Tags)

Protocol Number: UKI-001

Protocol Version: 2

Protocol Date: TBD

Protocol signature page

The undersigned has read and understood the trial protocol detailed above and agrees to conduct the trial in compliance with the protocol.

Principal Investigator Name	Principal Investigator Signature	Date	
(Please print)			

Protocol Section	Protocol Version 1	Protocol Version 2	Rationale
Section 3.1-3.2, 4, 6.2.1-6.2.3	Use of micro STR on 2-4 mm skin tags	Use of micro STR on approximately 4-6mm skin tags	The micro STR band has not reached the desired level of efficacy on 2-4mm skin tags per use under protocol version 1. The Sponsor recommends the use of a micro STR band to be placed on larger skin tags, 4-6mm, where they may be more effective at restricting blood flow to the skin tag and removing the tag.
Section 6.2.4, 6.2.6	Daily eDiaries Day 1-10	Daily eDiaries at screening visit, Day 1-20	An eDiary has been added to the screening visit to capture a photo of the skin tag at the time of banding. The number of daily diaries have been extended to 20 days to allow tracking for skin tags which may fall off after day 10.
Section 6.2.4	Virtual Visit 2 window Day 5-8	Virtual Visit 2 window Day 5-9	Visit window was extended to allow for more time to conduct the visit with no impact to patient safety
Section 6.2.4	Virtual Visit 3 window Day 11-14	Virtual Visit 3 window Day 21-24	The visit was moved to one day after the last daily diary completed by participants, which is now day 20 under protocol version 2.
Section 6.2.1	6.2.1 Stratification schematic to reflect 1:1 ratio of micro:standard STR device type	6.2.1 Stratification schematic to reflect 3:1 ratio of micro:standard STR device type	Due to micro and standard devices not reaching desired level of success in removing skin tags for 2-4 and 4-6 mm, respectively, the new recruitment efforts will focus on large skin tags and use of the micro device only
Section 4	Indications for use statement per device type	General indications for use statement to be determined upon completion of the study	Indications for use have been updated to be determined upon competition of the study
Section 6.2.1	80% compliance for eDiary completion to	participant payment of \$10 per eDiary completed	Participant compensation has been changed from overall compliance calculation to daily diary completion

			Tieaitii
	receive \$100 payment		to increase retention & eDiary completion through Day 20
Sections 6.2.3; 6.2.6	Rebanding not permitted; participants were withdrawn if device detached prematurely.	Participants may receive up to two rebanding visits per skin tag at the site in the event of premature device detachment. Rebanding details (e.g., timing, outcome) will be captured in the eDiary.	To allow controlled reapplication of the device and preserve participant data in cases of device failure, while maintaining consistency in study execution and analysis.
Section 6.2.3	No bandage was used after device placement.	A small adhesive bandage is applied at the screening visit to cover the banded skin tag. Participants receive approximately 20 bandages and instructions for replacement as needed.	To reduce risk of premature band detachment due to friction from clothing and improve retention of the device throughout the study period.
Section 6.2.1	No guidance on re- enrollment of prior participants	Participants previously enrolled may be re- enrolled if a different, previously unbanded skin tag is selected	To allow enrollment of individuals who meet inclusion criteria and had a device failure in a prior protocol version, without compromising data integrity
Sections 6.1, 14	The observed percentage of successful removal is 80%	The observed percentage of successful removal is 60%	Updated to reflect realistic expectations of effectiveness in a real-world setting.
Section 11.2	Not included	New section on withdrawal for non- compliance (e.g. missed rebanding)	Ensures clear criteria for withdrawal tied to study adherence.

TABLE OF CONTENTS

2. SUMMARY AND BACKGROUND INFORMATION

2.1. Skin tag background

The occurrence of potentially life-threatening malignant neoplasia in the skin has focused the public to address skin abnormalities, especially when they deviate from the skin's normal appearance. This produces an opportunity for early detection, by the patient and their physician, of potentially dangerous neoplasms such as malignant melanoma, squamous cell cancer and a long list of other rare neoplasms. However, the vast majority of skin lesions are benign, prompting many individuals to pursue options for the removal of lesions for cosmetic reasons.

Common benign skin lesions include verruca, seborrhea , keratoses, fibromas, histiocytomas (dermatofibromas), nevi and skin tags (acrochordons). A skin tag is a small outgrowth of epidermal and dermal tissue. Their size can range from one to several mm; usually flesh-colored and pedunculated (see Image 1)¹. Skin tags are exceedingly common benign skin lesions with a reported prevalence of around 45–50% in the general population. Typically, they are small, soft, noncancerous fibromas or fibroepithelial polyps, bumps of tissue connected to the skin's surface by a narrow stalk. The color, texture, size, and width of the base can vary².

While the exact cause of skin tags is not known, they can be found around folds of the skin or where areas of friction from clothes occur. Elevated blood sugar and insulin are linked to higher prevalence, but the mechanism, in this case, is still unknown. Some skin tags can become irritated, the most common motivation for removing skin tags is cosmetic.

Tags can be removed by a dermatologist using excision, cauterization, or cryosurgical means, but

pg. 6 of 30 Confidential

¹ Image from product's UK labeling

² My Face Aesthetics Clinic: Skin Tags

there is a growing interest in home-based methods. Some devices, such as cryo-based cauterization, have been cleared for marketing by FDA for "over-the-counter" (OTC) use and claimed acceptable removal levels.

Patients are motivated to remove skin tags, but the health care infrastructure is often less interested because skin tags are benign, and the cost of a clinical intervention can be hard to justify, regardless of the psychological impact on the patient. Skin anomalies such as skin tags may strongly affect the patient's quality of life. Even slight changes in the skin may result in adjustments to social life, relationships, and even the ability to carry out daily tasks.

Histologically, a skin tag shows localized hyperplasia of the dermis with loosely arranged collagen fibers and dilated capillaries and lymphatic vessels³, indicating that a skin tag is softer, more elastic, and about as vascularized as the surrounding skin. The epidermis can be slightly hyperplastic.

The cellular characteristics of the skin tag are important from the point of view of removal by pressure at the base. Externally exerted pressure would result in little resistance from the tissue, and the vasculature would easily collapse. These lesions tend to be smaller. However, the presence of nevus cells and a firm connective tissue network may protect the vasculature at the base from pressure. These lesions are often larger, broader in base, and "dome-shaped" and exert more resistance to compression of the base.

The current device and study are based upon the mechanism of action that includes an occlusion of the vasculature at the base. This action results in a necrosis of the skin tag. When occlusion of the base is complete, the necrosis leads to the tag simply falling off.

2.2. Purpose of Investigative Study

The aim of this study is to investigate the safety and effectiveness of a mechanical device to remove skin tags in adults. The device utilizes the ligation method by applying a silicone band around the base of a skin tag, therefore restricting the blood supply, which is vital to its growth and survival. Because this method does not include freezing or burning of tissue in or around the skin tag, it could be considered less invasive and less risky than other options.

A clinical validation study to demonstrate the safe and effective removal of skin tags will be completed under the direction of an investigator (dermatologist or other health care professional) led protocol. This study will assess the proportion of skin tags successfully removed within a 20-day period, and to evaluate associated safety outcomes. Adult (22 years and above) subjects fitting the inclusion/exclusion criteria will be recruited, given they have one or more skin tags consistent with device labeling. All subjects entering the clinical study will have the device applied by the healthcare professional and proceed through the study, recording their experience using an electronic clinical diary to collect data.

Since this device is to be sold over-the-counter, evaluation of the subject's self-selection and label comprehension abilities will be completed under a separate Human Factors and Usability study and is therefore not required in the scope of this clinical trial.

3

³ UC Davis Dermatology Online Journal

3. STUDY DEVICE NAME AND DESCRIPTION

3.1. Study Device Name: Skin Tag Remover (STR)

For this Protocol, the study device will be referred to as "Skin Tag Removal" study device or "STR" study device. There are two versions of the STR study device, automatic and manual. Each version is also manufactured in two sizes which correspond to the size of the skin tag to be removed.

Under protocol version 1, t he smaller size (to be referred to as "micro" for the remainder of this document) is designed to be used with skin tags having a base measuring between 2–4mm. The larger size (to be referred to as "standard" for the remainder of the document) is to be used with tags having a base measuring between 4–6 mm.

Under protocol version 2, the micro size band will be used on all skin tags measuring between 4-6mm. The standard size will no longer be used and skin tags measuring between 2-4mm will not be enrolled.

Product labeling has a helpful guide for determining size of band to use. All four versions function in the same manner by placing a band at the base of the skin tag, therefore, this document will collectively refer to all four iterations of the study device as "STR."

3.2. General Description of Study Device

The STR study devices are designed for the removal of skin tags from the body by ligation of the blood supply to the skin tag through the application of a small elastic band. Bands are placed around the base of the skin tag by using an applicator, which pushes the band from a cylindrical extension on the device over the skin tag and to the base of the tag.

The study device(s) are available in two different sizes to ensure the bands being used are tight enough to restrict the blood supply for skin tags that vary in size⁴.

- Under protocol version 1: The micro version of the STR study device has been designed to remove skin tags that measure 2-4mm at the base, and the standard version is designed to remove skin tags that measure 4-6mm at their base. When determining band size, it is suggested to use the smaller (micro) device for tags that are in-between micro and standard for best results.
- Under protocol version 2: The micro size will be used on skin tags that measure 4-6mm at their base. The standard size will not be used. Additional Skin tags measuring 2-4mm will not be enrolled.

_

⁴ Image from product's UK labeling

For general information about this device, currently sold in the UK, please reference https://tagband.co.uk.

3.2.1. Device Kit Description

The STR study device(s) for this study are provided in kits containing:

- STR study device
- Band loader
- Ten (10) bands
- Isopropyl alcohol (70%) cleansing swabs (4) used to cleanse the skin tag and surrounding area before applying the band

In addition to the study device kits, the site will receive packages of ~30 bandages for each skin tag expected to be included in this study. These bandages will be provided to the participant at their in-clinic Baseline Visit.

4. INDICATIONS FOR USE STATEMENT

Micro Versions - Manual and Automatic: The STR device is indicated for the OTC treatment/ removal of skin tags with a diameter of 2-6 mm at the base. Use of the device will be restricted from skin tags in sensitive areas of the body such as on eyelids, near the eye, or in the groin area. The STR device is for use by adults 22 years of age or older. Micro Versions will now be used on all skin tags with a diameter of 4-6mm at the base under protocol version 2. Skin tags measuring 2-4mm will no longer be enrolled.

Standard Versions - Manual and Automatic: The STR device is indicated for the OTC treatment/ removal of skin tags with a diameter of 4-6mm at the base. Use of the device will be restricted from skin tags in sensitive areas of the body such as on eyelids, near the eye or the groin area. It is for use by adults 22 years of age or older. Standard versions will not be used under protocol version 2.

The statements above were only the intended Indications For Use of the STR Device.

Instructions For Use documents are provided to the Investigator for each study device and size.

5. REPORT OF PRIOR TESTING

The STR study device has been designed and manufactured following ISO13485 Quality Management. Sponsor management has implemented a Quality Management System during the design of the device and followed it through manufacturing. Failure modes for design/production (DFMEA and

PFMEA) processes have been completed and evaluated and are a part of the Design History File (DHF).

In preparation for clinical testing, the STR study devices have completed testing regimens to document conformity to normalized standards, including ISO-10993 Biocompatibility. Biological testing for this device was completed in 2022 and a Biological Evaluation Report is available for review by contacting the Sponsor.

6. INVESTIGATIONAL PLAN

The Sponsor has developed the following investigational plan to clinically evaluate the safety and efficacy of the STR study device to remove skin tags from adult participants.

6.1. Purpose and Study Arms

This pivotal investigational study is designed to evaluate the safety and efficacy of a skin tag removal (STR) study device. This is a non-significant risk interventional clinical study that will be conducted by a Clinical Research Organization (CRO) with a licensed dermatologist(s) to serve as Principal Investigator. There are two arms of the study that are only differentiated by the type of STR study device used; arm 1 will be conducted using the manual version, and arm 2 will use the automatic version.

After consultation with the FDA, the Sponsor has modified the original protocol to include the following changes:

- Exclusion of all skin tags located around the eye, on the eyelid, or the groin area (6.2.1)
- Clarification of covered medical expenses while enrolled in the study (6.2.4)
- Protocol includes updated exclusion conditions (excluding those with known hypertrophic scarring or keloid scarring)
- Protocol includes the addition of an electronic daily diary for all participants
- A study was conducted to power the investigation for biostatistical relevance properly (please see the report in the Reference section). The conditions for power analysis were:
 - The primary endpoint is the removal of the skin tag (effectiveness)
 - The observed percentage of successful removal is 60%; i.e. 60% of the skin tags treated are expected to be successfully removed with use of the device
 - A 95% Confidence Interval (CI) was used to determine the number of subjects necessary for participation

Determination: if a successful clinical trial is established at 60% of treated skin tags removed, a study powered with 200 treated tags will have a 95% confidence interval of 5.5%

The power analysis determined that the sponsor should enroll enough subjects to treat a total of 200 skin tags. Typically, patients seeking skin tag removal have from 1 to 5 tags that could be treated for removal, however, for this study, only a maximum of 2 tags per person will be treated. Therefore, the number of tags for intention to treat (ITT) in each arm is 100 for a study total of 200 tags. This approach will ensure that the study has been powered to a 95% confidence interval of 5.5%.

Approximately two thirds of the subjects in each arm are to receive micro bands (2-6 mm skin tags treated), while the other one third is to receive standard size bands (4-6mm size skin tags treated). The PI will manage the number of treated skin tags such that a variety of locations on the body (face, neck, arms, and torso) are represented in the study.

Under Protocol Version 1:

Arms	Assigned Interventions
Arm 1 – Manual Version Goal: successful removal of 60% of the skin tags treated with the STR device. Subjects will have up to two (2) tags treated, therefore, 50–100 subjects are anticipated for this arm. A total of 100 skin tags is the ITT (intention to treat).	Subject treatment data collected on: • Band size; 2-4mm (micro), or 4-6mm (standard) • Subject pool divided ~equally by band size • All skin tags will be banded by a healthcare professional
Arm 2 – Auto Version Goal: successful removal of 60% of the skin tags treated with the STR device. Subjects will have up to two (2) tags treated, therefore, 50-100 subjects are anticipated for this arm. A total of 100 skin tags is the ITT (intention to treat).	Subject treatment data collected on: • Band size; 2-4mm (micro), or 4-6mm (standard) • Subject pool divided ~equally by band size • All skin tags will be banded by a healthcare professional

Under Protocol Version 2:

Arms	Assigned Interventions
Arm 1 – Manual Version Goal: successful removal of 60% of the skin tags treated with the STR device. Subjects will have up to two (2) tags treated, therefore, 50–100 subjects are anticipated for this arm. A total of 100 skin tags is the ITT (intention to treat).	Subject treatment data collected on: Tag size; 4-6 mm (micro band) All skin tags will be banded by a healthcare professional

Arm 2 - Auto Version

Goal: successful removal of 60% of the skin tags treated with the STR device. Subjects will have up to two (2) tags treated, therefore, 50-100 subjects are anticipated for this arm. A total of 100 skin tags is the ITT (intention to treat).

Subject treatment data collected on:

- Tag size; 4-6 mm (micro band)
- All skin tags will be banded by a healthcare professional licensed dermatologist

For subjects meeting the inclusion/exclusion criteria and entering the study and having two skin tags being treated as a part of this study, please see the study design details on how both skin tags are to be treated in Section 6.2 below.

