14. BIOSTATISTICIAN POWER ANALYSIS

Confidence intervals were calculated based on the following specifications:

1. Endpoint: Skin Tag Removal

2. Observed percentage = 60%, 65%, or 70%

3. Sample Size: 25, 50, 75, 100, 125, 150, 175, or 200

4. Normal approximation 95% Cls

The confidence intervals are presented in Table 1.

Table 1: Confidence Intervals for Skin Tag Removal

Sample size	95% Confidence intervals for selected observed success rates*				
	60%	65%	70%		
25	.42 to .78	.47 to .83	.50 to .90		
50	.45 to .75	.51 to .79	.57 to .83		
75	.48 to .72	.54 to .76	.59 to .81		
100	.50 to .70	.55 to .75	.60 to .80		
125	.51 to .69	.56 to .74	.61 to .79		
150	.52 to .68	.57 to .73	.62 to .78		
175	.53 to .67	.58 to .72	.63 to .77		
200	.54 to .66	.59 to .71	.64 to .76		

^{*}Using Binomial exact method

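### Section 6.1 uses 60% both as the expected removal rate and as the success level, and calls the study powered although only confidence-interval widths were computed

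*Protocol*

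**What the plan says.** All the statements on expected rate and goal are in Protocol Section 6.1, in current version 2 text.

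- Expected rate: "60% of the skin tags treated are expected to be successfully removed with use of the device".
- Success level for the study: "if a successful clinical trial is established at 60% of treated skin tags removed, a study powered with 200 treated tags".
- Goal of each arm, in the same words for the manual and the automatic device: "Goal: successful removal of 60% of the skin tags treated with the STR device".
- Size: "the sponsor should enroll enough subjects to treat a total of 200 skin tags", and "the number of tags for intention to treat (ITT) in each arm is 100 for a study total of 200 tags".
- Basis of the size: "A 95% Confidence Interval (CI) was used to determine the number of subjects necessary for participation", summed up as "This approach will ensure that the study has been powered to a 95% confidence interval of 5.5" percent.

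Section 14 is headed as a power analysis. It contains only 95% confidence intervals for observed rates of 60%, 65% and 70% at sample sizes from 25 to 200. Neither section gives a null rate, a performance goal below the expected rate, a test, or a power figure.

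**The concern.** A success level needs some distance from the rate the device is expected to achieve. Where the two coincide, a device that performs exactly as planned reaches the level about half the time, because the observed proportion falls on either side of its expected value with roughly equal chance. Larger numbers narrow the interval but do not change this.

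The wording also carries more than the calculation supports. Section 6.1 describes the study as pivotal and as powered, so a reader may take it that 200 tags give a good chance of success. What was computed is how precisely the rate would be estimated.

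Two things are at stake. A device that works as assumed may be recorded as having missed its goal. And an arm may meet its goal on data that do not exclude a much lower true rate.

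**Working it through.** **Inputs.** Expected rate 60%, success level 60%, 200 tags in total, 100 per arm and at most 2 tags per subject (Section 6.1). Section 14 names the normal approximation ("Normal approximation 95% Cls"), while its table footnote names the exact binomial method. Independence of tags is an assumption, examined in step 4.

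**1. The Protocol's own figure.** The half-width of a normal-approximation 95% interval is 1.96 × √(p(1−p)/n). At p = 0.60 and n = 200 it is 1.96 × √(0.24/200) = 0.068, not 0.055. The exact interval for 120/200 is 0.529 to 0.668. The value 5.5% appears at p = 0.80: 1.96 × √(0.16/200) = 0.0554, and 80% is the rate that the change table gives for version 1. This is a separate error, and the point below does not depend on it. It does confirm that the stated basis of 200 tags is an interval width.

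**2. Chance of meeting the goal at a true 60%.** This takes success as an observed proportion of at least 60%; X is binomial.

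| Reading | Event | Probability |
|---|---|---|
| Pooled | X ≥ 120 of 200 | 0.531 |
| One arm | X ≥ 60 of 100 | 0.543 |
| Both arms (rule not stated) | 0.543² | 0.295 |

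The pooled goal is therefore missed with probability 1 − 0.531 = 0.469. If the goal meant strictly more than 60%, the three figures would be 0.473, 0.462 and 0.214. If it meant that the exact lower 95% limit must exceed 60%, 134/200 would be needed, with probability 0.025. The reading with at least 60% observed is the one most favourable to the sponsor.

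**3. What a pass would show.** The exact 95% interval is 0.529 to 0.668 for 120/200, and 0.497 to 0.697 for 60/100. An arm can thus meet its goal without excluding 50%. At a true rate of 55%, the observed-proportion rule is met with probability 0.088 on 200 tags and 0.183 on 100.

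**4. Two tags per subject.** If every subject contributes two tags and the within-subject correlation runs from 0 to 1, the step 2 figures stay within 0.524 to 0.543 pooled, 0.534 to 0.561 for one arm, and 0.285 to 0.315 for both arms. Correlation hardly matters here because goal and expectation coincide.

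**5. A goal below the expected rate, for illustration only.** Take a performance goal of 50% (not a figure from the Protocol) and require the exact lower two-sided 95% limit to exceed it. With two tags per subject and correlation ρ, effective n = 200/(1 + ρ). An assumed ρ of 0.3 gives 200/1.3 ≈ 154; ρ = 1 gives 100.

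| Effective n | Removals needed | Power at a true 60% |
|---|---|---|
| 200 (pooled, independent) | 115 | 0.787 |
| 154 | 90 | 0.685 |
| 100 (full correlation, or one arm of 100 independent tags) | 61 | 0.462 |

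Here correlation matters a good deal, so the power must be stated with its assumption.

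**The case against.** The strongest reply is that 60% is not a decision rule. The sentence in Section 6.1 is conditional and leads into an interval width, the arm tables speak of a goal, and no hypothesis test is described. On this view the trial is sized for precision, which is a legitimate basis for a single proportion, and the word powered is loose usage that promises no percentage. Any formal criterion may be in a statistical analysis plan that is not at hand.

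Much of this stands. The observed-proportion rule is an inference, so 0.53 and 0.54 must carry that condition. No numeric power is promised, so none is contradicted. The absence of a test from the Protocol is not in itself an error.

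A reader might also infer that the trial has only about a 30% chance of success. The documents do not support that. It requires both arms to reach 60%, and although each arm has its own goal, the 200 tags are presented as a combined total and the Protocol never states a joint rule.

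Nor is 0.53 a forecast for the trial as run. It supposes that every tag counted has a true rate of 60%. If version 1 tags count towards the 200, the chance could differ, since the change table reports that version 1 use fell short of the desired success. At a true 65% the chance would be about 0.94 pooled. And a pass at a true 55% is a false assurance only if 55% is unacceptable, which the Protocol does not say.

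What the reply does not remove is the text itself. If 60% is only descriptive, the words on when a successful trial is established are wrong. If it is a criterion, it equals its own expected value. An analysis plan can add a test, but it cannot separate 60% from 60% while both statements stand.

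**Conclusion.** The point holds in a limited form. Section 6.1 fixes a success level equal to the expected rate and describes as powered a study for which Sections 6.1 and 14 compute only interval widths. Judged on the observed proportion, with independent tags and a true rate of 60%, the goal is met with probability about 0.53 pooled or 0.54 in one arm, so a device performing as assumed misses the pooled goal about 47% of the time. These probabilities are robust to correlation within subjects but depend on the inferred rule and the 60% rate. The 0.30 figure is conditional on an unstated joint rule and should not be quoted as the trial's chance of success. The defect is in how the goal is set and described; a precision-based sample size is not wrong in itself.

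**What to change.** In Sections 6.1 and 14:

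- Replace the claim that the study is powered with a statement that 200 tags set the precision of the estimate only.
- Label 60% as the planning assumption, and remove it as the success threshold and arm goal.
- State success as the lower two-sided 95% bound, computed allowing for two tags per subject, exceeding a performance goal. That goal should lie below 60%, be justified by the sponsor, and be fixed before version 2 data are reviewed.
- Say whether the goal applies to the pooled tags or to each arm.
- Give the resulting power with its correlation assumption. With the illustrative 50% goal this would be about 79% for pooled independent tags, about 68% at an assumed effective n of 154, and about 46% at an effective n of 100 or for a single arm of 100.

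The change is one of wording and needs no extra patients. The sponsor must commit to a goal, and the stated power may look unfavourable. If the sponsor then wants higher power per arm or under strong correlation, that would need more subjects, which is a separate decision.

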6.2.1. Recruitment Population

For both arms of the study, subjects located in the U.S. will be recruited from the general population and/or through an invitation presented by the Principal Investigator or CRO. Potential participants may self-complete an IRB-approved online pre-screening survey. Every effort will be made to recruit well-represented subjects from the following groups:

- Age (22-50 and 51+)
- Sex assigned at birth (M/F)
- Race/Ethnicity
- Fitzpatrick Skin Type

The study cohort target is between 30 and 70 subjects per arm (depending on how many skin tags each subject presents for treatment), as determined by the power analysis.

Under Protocol Version 1, the study included two arms (manual and automatic STR application), and participants were treated with either the micro (2–4mm) or standard (4–6mm) sized band depending on the measured base width of the skin tag. Each arm included a roughly equal number of tags treated with each device size.

It is anticipated that some subjects will likely have several skin tags that could be treated with the STR study device. A maximum of two skin tags per subject may be chosen for treatment. For purposes of pooling the data more effectively, if a subject opts to have two skin tags treated in the study, the

following must apply;

- both skin tags must be of the same size; either micro (2-4mm); or standard (4-6mm).
 U nder protocol version 2, only skin tags measuring between 4-6mm will be banded with the micro size.
- both skin tags must be treated in the same arm (e.g. using the same STR study device, manual or automatic)
- skin tags must be in two different, distinguishable locations on the body (i.e. right side of neck and left armpit)

As of Protocol Version 2, only skin tags measuring 4–6mm at the base will be eligible for enrollment, and only the micro version of the STR device will be used. The standard-sized band will no longer be used in this version of the study. Participants may still have up to two eligible skin tags treated, provided both are within the 4–6mm size range, in different anatomical locations, and treated using the same device arm (manual or automatic).

Participants previously enrolled under an earlier version of the protocol may be eligible to reenroll, provided a different, previously unbanded skin tag(s) is selected for treatment. Skin tags previously banded are not eligible for rebanding under this protocol version.

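### Section 6.1 gives a 95% CI of 5.5% for 200 tags at 60% removal. The half-width at those inputs is about 6.8 points, and Table 1 is also too narrow there, under two conflicting method labels.

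*Protocol*

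**What the plan says.** Section 6.1 gives the inputs to the sample size. The rate is 60%: "The observed percentage of successful removal is 60%; i.e. 60% of the skin tags treated are expected to be successfully removed". The criterion is an interval: "A 95% Confidence Interval (CI) was used to determine the number of subjects necessary for participation". The result is a number of tags: "The power analysis determined that the sponsor should enroll enough subjects to treat a total of 200 skin tags". The section then states the precision twice: "a study powered with 200 treated tags will have a 95% confidence interval of 5.5"%, and "This approach will ensure that the study has been powered to a 95% confidence interval of 5.5"%.

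Section 14 holds the supporting table. Its fourth specification is "Normal approximation 95"% intervals, but the footnote to Table 1 reads "Using Binomial exact method". For 200 tags the table prints .54 to .66 at 60%, .59 to .71 at 65% and .64 to .76 at 70%.

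Section 6.2.1 adds: "A maximum of two skin tags per subject may be chosen for treatment".

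**The concern.** The half-width of an interval for a proportion follows from the rate, the number of observations and the confidence level. Section 6.1 gives all three, and 5.5 points does not follow from them. The table behind the statement does not give the right interval for the same case either, and its two method labels cannot both be true.

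Section 6.1 calls the study pivotal, and the protocol describes no hypothesis test or other power calculation. The precision statement, with Table 1 behind it, is therefore the whole quantitative case for 200 tags. As written it promises more precision than the design delivers. At an observed 60%, a reader would expect a lower limit of 54.5%, when it is about 53%.

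**Working it through.** **Inputs.** From Section 6.1: p = 0.60, n = 200 tags over both arms, 95% confidence. Sidedness is not stated, so two-sided is assumed. The 5.5% is read as a half-width. Read as a full width it would be further off, since the full width is 2 × 6.8 = 13.6 points.

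**Attempt to reproduce 5.5.** Normal approximation: 1.96 × √(p(1 − p)/n).

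- p = 0.60: 1.96 × √(0.24/200) = 0.0679, so 53.2% to 66.8%.
- Exact (Clopper-Pearson), 120 of 200: 0.5285 to 0.6685, half the width 0.0700.
- Other two-sided 95% methods, half the width: Wilson and Agresti-Coull 6.73 points, Jeffreys 6.75, continuity-corrected normal 7.04.
- One-sided 95%: 5.70 points.

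None gives 5.5.

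**Where 5.5 fits.** The normal half-width at n = 200 is 6.61 points at 65%, 6.35 at 70% and 1.96 × √(0.16/200) = 5.54 at 80%. The amendment log lists a change from 80% to 60% in Sections 6.1 and 14. The likely account is that the rate was updated and the dependent figure was not. The protocol does not say so, and the finding does not depend on it.

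**Tags needed for ±5.5 points at 60%.** n = 1.96² × 0.24 / 0.055² = 304.8, about 305 independent tags.

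**Table 1, n = 200 row.**

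| Rate | Printed | Normal | Exact |
|---|---|---|---|
| 60% | .54 to .66 | .5321 to .6679 | .5285 to .6685 |
| 65% | .59 to .71 | .5839 to .7161 | .5795 to .7159 |
| 70% | .64 to .76 | .6365 to .7635 | .6314 to .7626 |

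To two decimals, both methods give .53 to .67 at 60% and .58 to .72 at 65%, so both printed cells are too narrow. The 70% cell is right for the normal approximation; the exact lower limit would be .63.

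**Rest of Table 1.** Compared at two decimals, 14 of the 24 cells do not match the normal approximation. In 10 cells the rate implies a fractional count (65% of 25 is 16.25), so the exact method has no unique value there. Of the 14 cells with a whole count, 8 match neither method: n = 25, 50 and 75 at 60%; n = 100 at 65% and 70%; n = 150 at 70%; n = 200 at 60% and 65%. Against the normal interval, each of the eight is off by .01 at each limit. Three are too narrow (n = 25 at 60%, and the two at n = 200) and five too wide. Every printed interval is symmetric about its rate, which exact intervals at these rates generally are not.

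**Two tags per subject.** All the figures above treat tags as independent. With k subjects contributing two tags and a within-subject correlation r, the half-width is 1.96 × √(0.24 × (200 + 2kr)) / 200. The protocol gives no r; 0.2 to 0.5 is an assumption.

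- 150 subjects (k = 50): 7.1 points at r = 0.2, 7.6 at r = 0.5.
- 100 subjects (k = 100): 7.4 points at r = 0.2, 8.3 at r = 0.5.

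**The case against.** The strongest reply is that nothing in the study turns on the figure. The goal is an observed removal rate of 60%, no acceptance limit is tied to a confidence bound, and the gap is 1.3 points. The table's n = 100 cell at 60%, which is the per-arm case, is right under both methods. This is true, and it is why the remedy is a restatement and not more enrolment. It does not make the stated figure correct, and that figure is the one offered to justify the sample size.

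Second, Table 1 may not differ from 5.5 at all. Printed to two decimals, .54 to .66 would also arise from 60% ± 5.54 (.5446 to .6554). That is fair. The table shows ±6, but at this cell it could be the same number rounded. The neighbouring rows do not follow an 80% calculation, however: at n = 175 that would give 5.9 points, and the table shows 7. On either reading the cell cannot be reconciled with 6.8.

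Third, within-subject correlation is commonly left to the SAP, which is not at hand. Also fair. The clustering range rests on assumed correlations and does not measure the error; it only shows that 6.8 is a best case if a subject's tags are positively correlated.

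Finally, the footnote names the exact method as plainly as the specification names the normal one. Either can be kept, but not both.

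**Conclusion.** The concern holds. At its own inputs, Section 6.1 should give ±6.8 points (53.2% to 66.8%, normal approximation) or 52.9% to 66.8% (exact), not 5.5. Table 1 is too narrow at n = 200 for 60% and 65% under both methods that Section 14 names, and those two labels contradict each other. A reader finds 5.5 in Section 6.1, 6 as printed in Table 1, and 6.8 to 7.0 on calculation. The result assumes a two-sided 95% interval, 5.5% meant as a half-width, and independent tags; positive correlation between a subject's two tags would widen the interval further. This should be corrected, because the figure is the protocol's stated reason for treating 200 tags.

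**What to change.** Name one method and use it throughout. The normal approximation is the simpler choice: Section 14 already specifies it, and it gives a value in all 24 cells. Remove the exact-method footnote and recompute the whole of Table 1; the n = 200 row becomes .53 to .67, .58 to .72 and .64 to .76.

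In both places in Section 6.1, replace the 5.5% with:

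> With 200 treated tags and 60% removed, the 95% confidence interval (normal approximation) is 53.2% to 66.8%, i.e. ±6.8 percentage points. This is a precision figure that treats tags as independent; it would be wider if the two tags of one subject are positively correlated.

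If the exact method is preferred, state 52.9% to 66.8%, recompute Table 1 by it, and list the whole-number counts used.

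The cost is a wording and table correction, with no change to enrolment or procedures. The stated precision becomes about 1.3 points less favourable (6.8 − 5.5).
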